15.4. Sensitivity Analyses for Efficacy Endpoints

15.4.1. Per-Protocol Analyses

The primary and key secondary endpoints will be analyzed using the PPS with the same methodology.

15.4.2. On-Treatment Analysis

An on-treatment analysis will also be conducted for primary time to 4-component MACE (MACE-4) and 3-component MACE (MACE-3) endpoints in the PPS.

The sensitivity analyses will also be performed for the time to first occurrence of NODM on treatment for patients with baseline glycemic status of no diabetes, prediabetes, or normoglycemic in the PPS.

For these on-treatment analysis, events (MACE-4, MACE-3 or NODM) that occurred after DLDOSE + 30 days will be ignored. Patients who did not have events before that will be censored at the earlier of the DLDOSE + 30 days and DLASMT, the date of censoring for non-fatal events defined in Section 7.2.5.

[figure not shown]
On-treatment analyses will be performed for lipid parameters and biomarkers including LDL-C, HDL-C, non-HDL-C, total cholesterol, triglyceride, hs-CRP, HbA_{1C} and fasting glucose. For these endpoints, values measured more than 7 days after the Date of Last Dose of IMP will be excluded, and only observed values prior to that will be summarized by treatment groups, and for HbA_{1C} and fasting glucose also by baseline glycemic status.

15.4.3. Adjunctive Cross-in Lipid-Modifying Therapy

Post randomization, LDL-C results will be masked for investigators and study participants in order to maintain the blind. Beginning at Month 6 (Visit T4) and for the remaining duration of the study, the central laboratory will notify the investigator if the patient's LDL-C level is $\geq 25\%$ higher than baseline LDL-C. The patients will be counseled on healthy dietary guidelines and reminded to take all lipid-regulating medications. The patient will return to the clinic for a repeat fasting blood lipid sample to confirm that the LDL-C value meets the threshold criteria. If confirmed, the patient's LDL-C-lowering treatment regimen may be adjusted, if possible, per standard of care and local practice. Any initiation and/or dose change of LDL-C-lowering medications will be documented on the electronic case report form (eCRF) and will not be provided by the Sponsor.

The use of adjunctive cross-in LMTs may obscure the difference between the treatment groups. To evaluate the treatment effects without cross-in LMTs, a sensitivity analysis will be performed for MACE-4 (primary) and MACE-3 endpoints in the PPS prior to cross-in LMT. Specifically, the patients are censored at the earlier of the date of starting the first cross-in adjunctive LMT therapy + 30 days and date of censoring for non-fatal events defined in Section 7.2.4, if there is no MACE-4 or MACE-3 event prior to that date.

For LDL-C and hs-CRP, observed values in changes and percent changes from baseline to Month 6 will be summarized by treatment group in the PPS, after excluding values measured after 7 days post the date of starting the first cross-in adjunctive LMT therapy.

15.5. Exploratory and Descriptive Analyses of Efficacy Endpoints

15.5.1. Subgroup Analyses

The primary endpoint (MACE-4) and time to 3-component MACE (MACE-3) will be analyzed within the subgroups below using FAS and the same primary analysis method previously described. The treatment and subgroup interaction will be examined by including the interaction term in the Cox PH model, and the p-values will be reported. Forest plots for the primary efficacy variable (hazard ratios) will also be presented.

- Age category (<65 years, ≥65 to <75 years, and ≥75 years)
- Race (White vs Non-white)
- Ethnicity (Hispanic or Latino vs No Hispanic or Latino)
- Sex (male vs female)
- Region (North America, South America, Western Europe, Eastern Europe, Other)
- BMI category (<25 kg/m², 25 to <30 kg/m², and ≥30 kg/m²)
- Baseline CVD risk category (Secondary vs Primary prevention)
- Baseline LDL-C category (<130 mg/dL, ≥130 mg/dL and <160 mg/dL, ≥160mg/dL)
- Baseline hs-CRP category (<2 mg/dL and ≥2 mg/dL)
- Baseline eGFR category (≥90; ≥60 to <90; and <60 mL/min/1.73m²)
- Baseline CKD history (Yes vs No)
- Baseline glycemic status (normoglycemic, prediabetes, or diabetes)
- Baseline ezetimibe use (Yes vs No)
- Baseline statin use (Yes vs No)
- Statin intolerance criteria (Failed 2 or more statin, vs otherwise)

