8.3. Multiplicity

There are one primary and six key secondary efficacy endpoints of interest for statistical testing in this study. A gatekeeping or hierarchical approach is used to test the primary efficacy endpoint and then key secondary efficacy endpoints sequentially to preserve the study-wise Type I error rate at 5%. For each endpoint, the null hypothesis is that of no difference between bempedoic acid and placebo groups, and the order for the hierarchical testing is:

1. time to first occurrence of MACE (CV death, nonfatal MI, nonfatal stroke, or coronary revascularization; primary 4-component MACE)
2. time to first occurrence of the composite endpoint of CV death, nonfatal MI, or nonfatal stroke (3 component MACE)
3. time to first occurrence of fatal or nonfatal MI
4. time to first occurrence of coronary revascularization

5. time to first occurrence of fatal or nonfatal stroke
6. time to CV death
7. time to all-cause mortality

For the final analysis of the differences between bempedoic acid and placebo, each hypothesis in this hierarchical order will be tested at a two-sided significance level of 0.05. Statistical significance at each step is required in order to test the next hypothesis. If any of the endpoints does not reach statistical significance, p-values for subsequent endpoints will be reported for information only.

For other efficacy and safety endpoints, a nominal p-value may be reported for information only.

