11. DEMOGRAPHIC AND BASELINE CHARACTERISTICS

Demographic data and other baseline characteristics will be summarized by treatment group for the FAS, SAS and PPS. These data will also be provided for patients in the SAS with baseline ezetimibe use. No statistical testing will be carried out for demographic or other baseline characteristics.

The following demographic and other baseline characteristics will be summarized and listed for this study:

- Age (years)
- Age category (<65 years, ≥65 to <75 years, or ≥75 years)
- Sex (female vs male, at birth)
- Race (American Indian or Alaska Native, Asian, Black or African American, Native Hawaiian or Other Pacific Islander, White, and Other)
- Ethnicity (Hispanic or Latino vs Not Hispanic or Latino)
- Region (defined in Section 7.5.1)
- Weight (kg)
- Height (cm)
- Body mass index (BMI) (kg/m^2) = $\text{weight (kg)}/\text{height (m)}^2$
- BMI category (<25 kg/m^2 , 25 to <30 kg/m^2 , or ≥30 kg/m^2).
- Baseline vital signs (systolic blood pressure, diastolic blood pressure, and heart rate)
- Baseline key laboratory Results (LDL-C, hs-CRP, Non-HDL-C, TC, HDL-C, and TG) (LDL-C results are presented in both conventional and standardized units, the others will be in conventional units only)
- Baseline LDL-C category (<130 mg/dL, ≥130 mg/dL and <160 mg/dL, ≥160 mg/dL)
- Baseline hs-CRP category (<2 mg/L, ≥2 mg/L)
- Baseline CVD risk category (Section 7.5.3), for patients with documented CVD history (secondary prevention), the prior history of CAD, PAD or CeVD.
- History of diabetes mellitus (Yes vs No, as collected in the *Targeted Cardiovascular History/Risk Factors* CRF)
- Baseline glycemic status (Section 7.4)
- History of hypertension (Yes vs No, Section 7.5.2)
- Alcohol consumption (Non-drinker, Former Drinker, or Current drinker)
- Tobacco use (Never used, Former user, or Current user)
- Baseline background lipid-modifying therapy (LMT) (Statin use including statin only or Statin + other LMT, other LMT without statin, or none, see also Section 7.6.1)

- Baseline statin intensity (none, very low, low, moderate, and high, see [Section 7.6.2](#) and [Appendix 5](#))
- Baseline ezetimibe use (Yes vs No)
- Statin intolerance criteria as collected on the *Statin Intolerance Criteria Compliance* CRF [REDACTED]
- Baseline estimated glomerular filtration rate (eGFR) category (≥ 90 mL/min/1.73m²; 60 to <90 mL/min/1.73m²; 30 to <60 mL/min/1.73m²; or <30 mL/min/1.73m²)

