15.5.2. Covariate Analyses

Covariate analyses of the primary (MACE-4) and time to 3-component MACE (MACE-3) using Cox PH model will be performed as supportive analyses. Baseline covariates listed in [Section 15.5.1](#) will be included in the model one at a time.

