16.3. Safety Laboratory Evaluations

The list of central laboratory assessments to be included in the outputs is included in the Table 4 of the Protocol (Section 12.1.6.1) and includes H_bA_{1c}. Urinalysis is not quantitative, and coagulation is measured at selected patients/visits only, and these will not be summarized.

In addition, eGFR will be calculated using the formula: $186 \times (\text{creatinine}/88.4)^{-1.154} \times (\text{age})^{-0.203} \times (0.742 \text{ if female}) \times (1.210 \text{ if Black})$, where creatinine is in μmol/L. Blood urea nitrogen (BUN)/creatinine ratio (BUN/Creatinine ratio) will also be calculated.

Summaries for all lab results will be included for the below analyses:

- Observed and change/percent change from baseline by analysis visit for hematology and blood chemistry measurements.
- Creatinine and eGFR will be summarized by treatment group and by baseline eGFR categories (<30, 30 to <60, 60 to <90, and ≥90 mL/min/1.73m²).
- Fasting glucose and HbA_{1c} will be summarized by baseline glycemic status, and by treatment group.

[figure not shown]
The analyses for shift tables from baseline to the worst post-baseline category or value are presented in Table 2. Note that for fasting glucose and HbA_{1c} the analyses will be by baseline glycemic status.

Table 2: Analyses for Shift Tables of Laboratory Parameters

Parameter	Categories (From Better to Worse)
Fasting glucose (by baseline glycemic status)	<51 mg/dL ≥51 to <100 mg/dL ≥100 to <126 mg/dL ≥126 mg/dL
H _b A _{1c} (by baseline glycemic status)	<5.7% ≥5.7% and <6.5% ≥6.5 to <7% ≥7%
Alanine aminotransferase (ALT)	Normal, High (> ULN)
Aspartate aminotransferase (AST)	Normal, High (> ULN)
eGFR	≥90 mL/min/1.73m ² ≥60 to <90 mL/min/1.73m ² ≥30 to <60 mL/min/1.73m ² <30 mL/min/1.73m ²
Uric acid (UA)	Low/Normal (combined) High (> 5.7 mg/dL for female, >7.0 mg/dL for male)

Lab abnormalities associated with AESIs are listed in Appendix 7 and will be summarized with the AESIs. In addition, for evaluation of potential Hy’s Law cases, a pairwise scatterplot will be created with the maximum (peak) post-baseline values of ALT or AST as multiples of the ULN, against the concomitant TB (also multiples of the ULN).

Other lab abnormalities of selected parameters are presented in Table 3 and the number of patients meeting each criterion will be summarized by treatment group.

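### SAP 15.5.1 cuts baseline hs-CRP at 2 mg/dL (20 mg/L) where Section 11 uses 2 mg/L, and Table 2 ranks fasting glucose below 51 mg/dL as the best category

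*SAP*

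**What the plan says.** **hs-CRP.** SAP Section 15.5.1 lists the subgroups for MACE-4 and MACE-3. One is "Baseline hs-CRP category (<2 mg/dL and ≥2 mg/dL". For every subgroup, "The treatment and subgroup interaction will be examined by including the interaction term in the Cox PH model", with p-values reported, and forest plots are planned for the primary endpoint. Section 15.5.2 reuses the list: each baseline covariate in it "will be included in the model one at a time". Section 11, which defines the baseline table, gives "Baseline hs-CRP category (<2 mg/L, ≥2 mg/L". Appendix 10 also states its hs-CRP flag in mg/L (above 10 mg/L).

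**Fasting glucose.** SAP Section 16.3 says that "shift tables from baseline to the worst post-baseline category or value are presented in Table 2". The category column of that table is headed "Categories (From Better to Worse". The fasting-glucose entry reads, in order, "<51 mg/dL ≥51 to <100 mg/dL ≥100 to <126 mg/dL ≥126 mg/dL", tabulated by baseline glycaemic status.

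**Standing of these outputs.** Section 8.3 confines formal testing to the primary and six key secondary endpoints, and adds: "For other efficacy and safety endpoints, a nominal p-value may be reported for information only".

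**The concern.** The hs-CRP line gives one named category two definitions a factor of ten apart. Under 15.5.1, every patient from 2 to below 20 mg/L moves from the high group to the low group. The subgroup hazard ratios, interaction p-value and forest-plot row would then not match the baseline table, and the upper group could be too small to say anything about effect modification. hs-CRP is also a secondary biomarker endpoint (percent change to Month 6), so readers are likely to look at this row.

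In Table 2, if lower always counts as better, one ordinary value displaces a low one when the worst category is chosen. The table would have a row for values below 51 mg/dL that its own rule leaves almost empty in both arms. Someone reading that table alone could take the empty row to mean that no low values occurred.

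**Working it through.** **1. Units.** 1 mg/dL = 10 mg/L, so 2 mg/dL = 20 mg/L. That is ten times the Section 11 cut and twice the Appendix 10 flag. No other place in the documents gives hs-CRP in mg/dL. The contradiction needs no assumption; steps 2 to 4 only show its possible size.

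**2. Size of the upper hs-CRP group.** The documents give no hs-CRP distribution. Assume log-normal values with median m and log-SD s. The fraction above cut c is f = 1 − Φ[(ln c − ln m)/s]. I used m = 1.5, 2.3, 3 mg/L and s = 1.0, 1.1, 1.2. Selected results:

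| m (mg/L) | s | ≥2 mg/L | ≥20 mg/L | Intended high group reclassified as low |
|---|---|---|---|---|
| 1.5 | 1.0 | 38.7% | 0.48% | 98.8% |
| 2.3 | 1.1 | 55.1% | 2.5% | 95.5% |
| 3 | 1.0 | 65.7% | 2.9% | 95.6% |
| 3 | 1.2 | 63.2% | 5.7% | 91.0% |

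Over all nine combinations, the upper group is 39-66% at 2 mg/L and 0.5-6% at 20 mg/L, and 91-99% of the intended high group is reclassified.

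**3. Events in the upper group.** Take the planned minimum of 1,620 primary events and let r be the event rate above the cut relative to below it. Then e = 1620·f·r/(f·r + 1 − f).
- r = 1: about 8-92 events at 20 mg/L, against 627-1,065 at 2 mg/L.
- r = 2: about 15-175, against 904-1,285.

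**4. What the interaction test could detect.** With 1:1 allocation, 80% power and two-sided 0.05 (1.96 + 0.84 = 2.80), the detectable ratio of hazard ratios is exp[2.80·√(4/e + 4/(1620 − e))]. For r = 1:
- at 2 mg/L: 1.32-1.34 (for example, e = 900 gives 1.32);
- at 20 mg/L: about 1.8 (e = 92) to 7.5 (e = 8). The upper end puts a normal approximation on about 8 events, so read it only as practically uninformative.

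**5. Table 2 applied literally.** The worst category is the furthest down the printed list.
- Post-baseline 48, 96, 101 mg/dL: tabulated under ≥100 to <126; the 48 is not shown.
- Baseline 90, post-baseline 45 and 95: tabulated under ≥51 to <100, as no shift.
- Baseline 90, post-baseline 45 and 48: tabulated under <51, which the header places above the baseline category.

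A patient reaches <51 only if every post-baseline value is below 51.

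**6. How empty that cell would be.** Full chemistry is drawn at Months 3, 6, 12 and then every 6 months; Month 1 has only ALT, AST, total bilirubin and CK. That gives 5, 8 or 10 post-baseline draws by Month 24, 42 or 57.5, not counting the End of Study draw. Assume 8 draws, 0.1% of draws below 51, and 7,000 patients per arm.
- Independent draws: ever below 51 = 7000·(1 − 0.999⁸) ≈ 56 patients; always below 51 = 7000·0.001⁸ ≈ 0.
- Beta-binomial with intraclass correlation 0.3: about 27 patients ever below 51, about 0.1 always below.

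**The case against.** **The hs-CRP line is an obvious unit slip.** The line above it gives LDL-C in mg/dL, Section 11 holds the intended definition, and a programmer would probably reuse that variable. Section 15.5 is headed exploratory and descriptive, and the covariate models are supportive. All of this is fair and limits the consequence. But Section 15.5.1 governs the subgroup analysis, and two prespecified cuts leave the choice open. Section 5.3 has the SAP finalised before database lock and unblinding, so a correction made then removes any question of a cut chosen afterwards.

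**The magnitudes rest on assumed inputs.** This is correct. The distribution, event-rate ratio, glucose prevalence and correlation are all assumptions. Actual draw counts will also vary with early discontinuation and with unscheduled visits, which Section 7.2.4 treats like scheduled ones. The figures show scale only.

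**Low glucose can be seen elsewhere.** Appendix 10 lists all values for any patient below 70 mg/dL. Visit summaries would show the minimum if the Section 8.6 statistics are applied, and adverse events are tabulated by preferred term. The protocol has an AESI category for hypoglycaemia with metabolic acidosis. Table 3 and Appendix 7, whose contents are not in the text available for review, may hold a by-arm count. This stands: nothing here shows that low glucose is lost from the report.

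**Table 2 is one-directional by design.** Glucose sits beside HbA1c, and taking highest as worst is coherent for tracking hyperglycaemia. That would justify a combined low/normal row, as the same table uses for uric acid. It does not explain a separate <51 row ranked best, when Appendix 10 flags low glucose as potentially significant.

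**Conclusion.** Both points hold as matters of text. The hs-CRP subgroup cut in Section 15.5.1 contradicts Section 11 by a factor of ten. Followed literally, it would move most of the intended high group (91-99% under the log-normal assumptions) into the low group, leaving an interaction test with little power. The Table 2 glucose order means that this one table cannot show a transient low value and ranks a move below 51 mg/dL from a normal baseline as an improvement.

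The reach is limited to exploratory subgroup and supportive covariate analyses and one descriptive safety table. The primary analysis, hierarchy, alpha and sample size are unaffected. Both items should be corrected, but neither threatens the trial's main conclusions.

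**What to change.** **Section 15.5.1.** Change the hs-CRP categories to <2 mg/L and ≥2 mg/L, as in Section 11, before unblinding. Section 15.5.2 then inherits the corrected cut.

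**Section 16.3, Table 2.** Tabulate fasting-glucose shifts twice, from baseline to the highest and to the lowest post-baseline category, by arm and baseline glycaemic status. If Table 3 or Appendix 7 already gives a by-arm count of low glucose, refer to it from Table 2 and take the <51 row out of the better-to-worse order. This is a change of tabulation only; it proposes no clinical glucose threshold.

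**Cost.** One unit correction and one extra table or cross-reference in the SAP. No new data are needed.

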15.5.2. Covariate Analyses

Covariate analyses of the primary (MACE-4) and time to 3-component MACE (MACE-3) using Cox PH model will be performed as supportive analyses. Baseline covariates listed in [Section 15.5.1](#) will be included in the model one at a time.

15.5.3. Total Event Analysis

Since non-fatal events (non-fatal MI, non-fatal stroke, and coronary revascularization) can happen multiple times during study follow-up, analyses of MACE-4, MACE-3, non-fatal MI, non-fatal stroke, and coronary revascularization as total (i.e., first and subsequent) events will also be performed in the FAS. When there are multiple events occurring on the same day, they will be ordered as described in Section 15.2.1, and the event times will be separated by 0.1 day so that every event time is unique. The censoring date after the last events or for patients who had no event is the DLASMT. Hazard ratio will be estimated by Andersen-Gill mean intensity

model (Andersen and Gill, 1982), with robust sandwich estimates of the covariance matrix (Lin and Wei, 1989).

15.5.4. Incidence Rates of Primary and Key Secondary Endpoints

In addition to the hazard ratio and 95% CI from Cox PH model, incidence rate (IR) as number of events per 100 person years, along with the total number of person years and difference in IR between groups with 95% CI's will be provided for primary endpoint and key secondary endpoints. For this analysis, the duration of exposure is defined to be from the date of randomization to the date of the 1st event or the date of censoring.

15.5.5. Additional Analysis of Adjudicated Events

[figure not shown]
For the adjudicated clinical events that occurred after randomization, discordance between the classification of the investigators versus that of the CEC will be tabulated by treatment in the FAS.

15.6. Tertiary and Exploratory Analyses for Lipid and Biomarkers Endpoints

15.6.1. Tertiary Lipid and Biomarker Endpoints

Tertiary lipids measurements including non-HDL-C, TC, HDL-C, and TG will be summarized for the FAS by treatment groups using observed values for each timepoint (baseline, Month 3, 6, 12, 18, 24, 30, 36, 42, 48, 54 and 60). For each parameter, the value of the parameter, change, and the percent change from baseline will be summarized by treatment group, and by analysis timepoints (Section 7.2.4). The results are presented in both conventional units and standardized units.

In addition, fasting glucose will be summarized similarly by treatment group, by analysis timepoints, and by baseline glycemc status (Section 7.4) for the FAS.

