15.7.3. Tertiary Lipid and Biomarker Efficacy Endpoints

Tertiary lipid and HbA_{1C}-related endpoints will be summarized and analyzed as needed. For each parameter at each time point, the value of the parameter, change and the percent change from baseline will be summarized by treatment group. The Mixed Model Repeated Measure (MMRM) analysis including factors of treatment group, time point (as a categorical variable), baseline value, and treatment group-by-time point interaction will be performed in the observed FAS data. The LSM and SE will be provided for each treatment groups, along with the placebo-corrected LSM, its 95% CI, and associated p-value as needed. A nonparametric analysis based on Wilcoxon rank sum test and H-L estimate of location shift will be performed in observed FAS data for percent change from baseline to Month 12 and end-of study in hs-CRP. Changes in HbA_{1C} will be assessed in patients in the Normoglycemia Efficacy Population, Prediabetes Efficacy Population, No Diabetes Efficacy Population, Diabetes Efficacy Population, and Inadequately Controlled Diabetes Efficacy Population.

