2.3. Tertiary Objective

- To evaluate the effect of long-term treatment with bempedoic acid 180 mg/day versus placebo on non-high-density lipoprotein cholesterol (non-HDL-C), total cholesterol (TC), high-density lipoprotein cholesterol (HDL-C), triglycerides (TG), HbA_{1C}, and fasting glucose

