changes from baseline, and percent changes from baseline between the treatment groups will be presented together with 95% CIs at each timepoint, as descriptive analyses with no imputation.

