15.3.4. Secondary Efficacy Endpoint HbA_{1c}

All efficacy analyses of HbA_{1c} will be carried out stratified by the baseline glycemc status in the FAS. The subgroup of patients with Inadequately Controlled Diabetes (ICDM) at baseline is of primary interest. The other subgroups include Diabetes (that includes ICDM as a subset), Prediabetes, Normoglycemic, and No Diabetes (Prediabetes and Normoglycemic combined).

Analysis for the change from baseline to Month 12 in HbA_{1c} will be analyzed similarly as LDL-C, with change from baseline as response, treatment group and baseline HbA_{1c} as covariates. There is no need to specify variance heterogeneity (no 'REPEATED' statement) and the default method for degrees of freedom calculation can be used. Fitted mean (LS means) changes from baseline for each treatment group will be calculated (with 95% CI) at baseline HbA_{1c} levels of 8% and 7% for ICDM and Diabetes, 6% for Pre-Diabetes and 5.5% for Normoglycemic and the combined No Diabetes groups. The estimated differences in changes from baseline between treatment groups will be provided with 95% CIs and p-values for testing of no difference.

Missing HbA_{1c} data at Month 12 will also be handled using PMM based on whether the patient was still on treatment at Month 12 (Day 365), similar to LDL-C above.

For tertiary endpoints of HbA_{1c} measured at all timepoints (Baseline, Month 3, 6, 12, 18, 24, 30, 36, 42, 48, 54, and 60), the observed values at each timepoint, and changes from baseline will be summarized by treatment groups. Differences of the changes from baseline between the treatment groups will be presented together with 95% CIs at each timepoint, as descriptive analyses with no imputation.

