15.3.5. Secondary Efficacy Endpoint hs-CRP

Due to the highly skewed distribution of hs-CRP, a nonparametric analysis based on Wilcoxon rank sum test will be performed for percent change from baseline to Month 6. Hodges-Lehmann estimate of location shift and its 95% CI will be provided. Only observed values will be used with no imputation.

For hs-CRP measured at other timepoints (Month 12, and End-of-Study, which is defined to be the last measurement of each patient), the observed values at each timepoint, and percent changes from baseline will be summarized by treatment groups.

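### The SAP replaces the Protocol's modelled tertiary comparisons with by-arm summaries or unadjusted differences, leaving part of a versus-placebo objective without a planned estimate

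*SAP*

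**What the plan says.** Protocol 15.7.3 names a model for the tertiary lipid and HbA1c-related endpoints: "The Mixed Model Repeated Measure (MMRM) analysis including factors of treatment group, time point (as a categorical variable), baseline value", plus a treatment-by-time interaction, fitted to observed FAS data. It reports LS means and the "placebo-corrected LSM, its 95% CI, and associated p-value as needed". For hs-CRP at Month 12 and end of study it plans a Wilcoxon rank sum test with a Hodges-Lehmann estimate. The same section opens more loosely, saying that these "endpoints will be summarized and analyzed as needed".

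The SAP handles them in four places.

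- Section 15.6.1: "Tertiary lipids measurements including non-HDL-C, TC, HDL-C, and TG will be summarized for the FAS by treatment groups using observed values for each timepoint". Fasting glucose is summarised in the same way, also by baseline glycemic status.
- Section 15.3.3, LDL-C at all visits: differences between arms in change and percent change "will be presented together with 95% CIs at each timepoint, as descriptive analyses with no imputation".
- Section 15.3.4, HbA1c at all visits: "Differences of the changes from baseline between the treatment groups will be presented together with 95% CIs at each timepoint".
- Section 15.3.5, hs-CRP after Month 6: "the observed values at each timepoint, and percent changes from baseline will be summarized by treatment groups".

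The SAP's tertiary objective (2.3) begins "To evaluate the effect of long-term treatment with bempedoic acid 180 mg/day versus placebo on non-high-density lipoprotein cholesterol" and goes on to TC, HDL-C, TG, HbA1c and fasting glucose. Protocol 15.1 lets the SAP prevail where the two documents differ on analysis.

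**The concern.** An objective framed as an effect versus placebo needs a planned estimate of that effect. For non-HDL-C, TC, HDL-C, TG and fasting glucose, SAP 15.6.1 states none: no difference, no interval, no model. Silence there is hard to read as an implied comparison, because 15.3.3 and 15.3.4 say so explicitly when between-arm differences are wanted. Later hs-CRP also loses its Protocol comparison; it falls under the secondary objective in SAP 2.2, which is likewise about long-term effect versus placebo.

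For LDL-C and HbA1c at the tertiary visits there is a difference, but it sets aside the baseline value, which is already collected, and the patient's other visits. The SAP accepts the case for baseline adjustment elsewhere, since it adjusts LDL-C at Month 6 and HbA1c at Month 12.

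The practical stake is prespecification. SAP 5.3 requires added analyses to be marked as ad hoc, so a placebo-corrected estimate produced later for these endpoints would lose its planned status, although the Protocol had specified the model for the lipids. SAP 8.3 allows nominal p-values for other endpoints but names no method, which leaves that choice open.

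**Working it through.** **No design figure is at issue.** Neither document gives a precision or power figure for the tertiary endpoints. The 1620 primary events do not enter this point. As a check, the Schoenfeld formula gives 1592 events at HR 0.85, two-sided alpha 0.05 and 90% power, and 1620 events give 90.5% power. Nothing below alters that.

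**Step 1: planned methods side by side.**

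| Endpoint | Protocol | SAP | Between-arm estimate in the SAP |
|---|---|---|---|
| non-HDL-C, TC, HDL-C, TG | 15.7.3: MMRM with baseline | 15.6.1: by-arm summaries | None stated |
| Fasting glucose | Not named in the 15.7.3 MMRM | 15.6.1: by-arm summaries within glycemic status | None stated |
| hs-CRP, Month 12 and end of study | 15.7.3: Wilcoxon, Hodges-Lehmann | 15.3.5: by-arm summaries | None stated |
| LDL-C, tertiary visits | 15.7.3: MMRM with baseline | 15.3.3: differences with 95% CI | Yes; no baseline covariate named |
| HbA1c, tertiary visits | 15.7.3: MMRM with baseline | 15.3.4: differences with 95% CI | Yes; no baseline covariate named |
| LDL-C, Month 6 (secondary) | 15.7.2: ANCOVA, PMM | 15.3.3: linear model with baseline, PMM | Yes, adjusted |
| HbA1c, Month 12 (secondary) | 15.7.2: ANCOVA, PMM | 15.3.4: model with baseline in each glycemic group, PMM | Yes, adjusted |

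The on-treatment summaries (SAP 15.4.2) and safety laboratory summaries (SAP 16.3) are also by arm, so they do not fill the gap. No MMRM appears in the available SAP text.

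**Step 2: what leaving out baseline costs.** Let s be the common SD of the level at baseline and follow-up, and rho their correlation. The documents give no rho, so it is assumed, with a range.

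- Per-patient variance of the change score: 2s²(1 − rho).
- Per-patient residual variance after baseline adjustment: s²(1 − rho²).
- Ratio, unadjusted to adjusted: 2(1 − rho)/(1 − rho²) = 2/(1 + rho).
- Ratio of CI widths: the square root of that.

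| rho (assumed) | Unadjusted, in s² | Adjusted, in s² | Variance ratio | CI width ratio | CI wider by about |
|---|---|---|---|---|---|
| 0.3 | 1.40 | 0.91 | 1.538 | 1.240 | 24% |
| 0.5 | 1.00 | 0.75 | 1.333 | 1.155 | 15% |
| 0.7 | 0.60 | 0.51 | 1.176 | 1.085 | 8% |
| 0.9 | 0.20 | 0.19 | 1.053 | 1.026 | 3% |

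**Step 3: absolute scale.** With 7000 per arm, no missing values and rho = 0.5, the 95% half-width is 1.96 × √(2 × 1.00/7000) = 0.0331 SD unadjusted and 1.96 × √(2 × 0.75/7000) = 0.0287 SD adjusted. In the full FAS both are narrow. Within glycemic groups n is smaller and both widen, but their ratio stays the same.

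The algebra applies to absolute change with equal SDs. For percent change it is only indicative, and SAP 15.3.3 itself expects the variance of LDL-C percent change to differ between arms.

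**The case against.** **The change is permitted, and the Protocol text is hedged.** Protocol 15.1 gives the SAP precedence, and 15.7.3 applies its as-needed qualifier both to the analysis of these endpoints and to the contrast. Descriptive reporting of tertiary endpoints is a legitimate choice. This stands, but the same Protocol section also commits to performing the MMRM, and the SAP keeps an objective that by-arm summaries do not estimate. A reader might infer that the change was made without explanation. The documents do not show that, because parts of the SAP are absent from the available text.

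**Some relevant SAP text is not available.** The contents list 15.4.4 (additional diabetes analyses) and 15.6.2 (responder analyses), but their bodies are not in the available text, and SAP 7.4.2 refers to a Month 12 HbA1c sensitivity analysis that appears in none of the sections that are. A reader might infer that glucose has no comparison anywhere in the plan. That cannot be asserted; the claim is limited to the available sections.

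**HbA1c and LDL-C are covered at the main time points.** A reader might infer that these two have only unadjusted differences throughout. They do not: LDL-C at Month 6, and HbA1c at Month 12 in every glycemic group, keep baseline-adjusted pattern-mixture analyses.

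**Fasting glucose was not clearly in the Protocol model.** Correct. It comes under the MMRM only on a broad reading of HbA1c-related, so a model for it is an addition.

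**The MMRM would not cure dropout.** Also correct. It too used observed data, and its listed terms do not include treatment status. What it adds is baseline adjustment and use of a patient's other visits under missing-at-random. Some later absence is simply staggered entry. A reader might infer that the SAP's differences are biased by dropout; the documents do not establish that.

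**By-arm summaries let a reader form the difference.** The mean, SD and n by arm (SAP 8.6) do give an unadjusted difference and interval, but not a baseline-adjusted one.

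**Conclusion.** The point holds within limits. In the available text, the SAP states no between-arm estimate for non-HDL-C, TC, HDL-C, TG and fasting glucose, or for hs-CRP after Month 6. At the tertiary visits it names no baseline covariate for LDL-C and HbA1c differences. The Protocol had planned an MMRM for the lipids and HbA1c and a Hodges-Lehmann estimate for hs-CRP.

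The missing contrasts follow from the text and need no numerical assumption. The precision loss does: an interval about 24% to 3% wider for an assumed rho of 0.3 to 0.9, for absolute change with equal SDs.

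The consequence is small. These endpoints lie outside the testing hierarchy and their p-values are nominal. A reader might infer that the trial's main conclusions are exposed; they are not. No primary, key secondary or secondary inference, alpha or sample size changes.

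**What to change.** - In SAP 15.3.3, 15.3.4 and 15.6.1, restore the Protocol MMRM for LDL-C, non-HDL-C, TC, HDL-C, TG and HbA1c, reporting the placebo-corrected LS mean with 95% CI at each visit. Run HbA1c within baseline glycemic group. If the model does not converge, use ANCOVA on baseline at each visit.
- In SAP 15.6.1, add the same baseline-adjusted contrast for fasting glucose within glycemic group, and label it an addition rather than a restoration.
- In SAP 15.3.5, restore the Hodges-Lehmann estimate with 95% CI for hs-CRP at both Month 12 and end of study.
- Keep all p-values nominal.

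If the sponsor prefers descriptive reporting, the SAP should state that choice and its reason, and Protocol 15.7.3 should be aligned.

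The cost is SAP wording, additional output and computing time for a large repeated-measures model. No new data are needed.
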